#### Specific:

- Analyze the variation of the plantar dynamics in the subjects without intervention to avoid learning bias of the methodology of the baropodometric registry.
- Evidence if deep dry needling is effective in the treatment of myofascial trigger point.
- Observe if there are differences in the treatment taking into account the covariates measured such as age, sex, and physical activity practice and body mass index.

Volunteers who want to participate in the study will read the general information of the study and sign the informed consent to participate in the study.

Once the informed consent has been read and delivered, the evaluator will check that they meet the inclusion criteria. After the data collection, a randomization (Epidat V4.0) of the selected subjects will be carried out to assign them to one of the intervention groups.

In the evaluation room, the evaluator, after taking the measurements of weight and height.

To locate the myfascial trigger point in the tibialis psoterior, the palpation technique will be used, grasping the belly of the muscle between the thumb and the 2nd and 3rd fingers. The evaluator will press the fibers with a forward and backward movement to find the taut bands. Once the taut band is found longitudinally, the nodule and the point of greatest sensitivity to pressure will be located.

Once the myofascial trigger point is located, it will be marked with a dermal marker. Those subjects in whom the myofascial trigger point can not be located with precision, will be excluded from the study.

After having marked the myofascial trigger point, the evaluator will make the subject the algometry in the myofascial trigger point. 3 measurements will be taken with an interval of 20 seconds between measurement and measurement, and the average of the three measurements obtained will be calculated.

Next, The baropodometry will be carried out. The subject will perform the march on the platform for one minute. At the moment that the baropodometer registers correctly the data will warn us.

Once the pre-intervention measurements have been made, the subject will go to the adjoining room to carry out the intervention.

The intervention sequence varied depending on the group to which the subject "Group intervention 1" (G1),

- "Intervention group 1" (G1): the deep dry needling technique will be performed with a duration of less than one minute in the tibialis posterior.

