Initial position: The patient will be placed supine with an external rotation of the hip and slight knee flexion. The auditor is placed on the homolateral side.

Placement of hands: the auditor locates the myofascial trigger point in the tibialis posterior with the left hand on the inside, back of the tibia, and perform the technique with the right hand.

Technique: The inspector, with gloves, disinfects the area to be treated with 70° alcohol. Once the alcohol is applied, the intervenor locates and takes the myofascial trigger point and places the needle with the guide tube resting on the skin of the patient. The inspector holds the guide tube between the index and middle fingers lightly touch the needle with the index finger of the other hand to insert the needle perpendicularly into the skin, directing it towards the inspector's thumb. Once the needle is inserted subcutaneously, the guide tube is removed. The controller deepens the needle to myofascial trigger point, and makes fast inputs and outputs into it. The rapid exit is made to the subcutaneous cellular tissue, outside the muscle, but not outside the skin. Next, hemostasis is performed in the area. Once this hemostasis is completed, the patient is incorporated and dressed.

- "Control group (G2)": the simulated dry puncture technique will be performed.

Initial position: The patient will be placed prone. The interventor is placed on the homolateral side.

Technique: The patient lies on the stretcher without the trousers. The interventor, with the guide tube, simulates the technique of puncture in the right twin of the subject. The controller cleans the area with 70° alcohol. Once the alcohol is applied, he performs the simulated dry needling technique in a plane with his index and middle fingers with the guide tube. It is important that the subject has his head stuck in the hollow of the head of the stretcher throughout the technique to make a correct masking.

Next, a simulation of hemostasis is performed in the area. Once this simulation is finished, the patient is incorporated and dressed.

Once the intervention is done, the subject will return to the evaluation room to proceed to the evaluation immediately after the intervention (POSTINT), both algometric and baropodometric measurements. After these measurements, the subject will be summoned at the same time to return at 24 hours (POST24h) and at 72 hours (POST72h) to perform the corresponding algometric and goniometric measurements.

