This study will be carried out in two adjoining rooms, with a sufficient amplitude to offer freedom of movement, both to the evaluator and the auditor and the subject of the study.

In one of the rooms will be the evaluator to perform the measurements and collect the pre- and post-intervention values. In the adjoining room will be the controller, in charge of carrying out the corresponding intervention.

Between both rooms there are about eight meters of distance without steps or unevenness, and they will maintain an identical and constant temperature.

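### Evaluator blinding for algometry is neither stated nor secured, and the measured point is cleaned and needled in one arm only

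*Combined protocol and SAP*

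**What the plan says.** All the relevant text is in the Study Protocol Plan, in the procedures that follow the specific objectives and in the description of the setting.

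- **Marking and measuring.** The trigger point is found by palpation in every subject. "Once the myofascial trigger point is located, it will be marked with a dermal marker". Then: "After having marked the myofascial trigger point, the evaluator will make the subject the algometry in the myofascial trigger point". The value is the mean of three readings.
- **G1 (deep dry needling).** "The inspector, with gloves, disinfects the area to be treated with 70° alcohol". "The controller deepens the needle to myofascial trigger point, and makes fast inputs and outputs into it". After the needle work, "Next, hemostasis is performed in the area".
- **G2 (control).** "The interventor, with the guide tube, simulates the technique of puncture in the right twin of the subject". The alcohol wipe and the simulated hemostasis that complete the sham are described for that same area. No step at the marked tibialis posterior point is described for G2 during the intervention.
- **Who measures, and when.** The subject goes back to the evaluation room at once for algometry and baropodometry, and returns at 24 h and 72 h. On the roles: "In one of the rooms will be the evaluator to perform the measurements and collect the pre- and post-intervention values". A different person delivers the intervention in the adjoining room.
- **Masking.** The only sentence on masking concerns the position of the subject's head during the sham. The protocol and SAP say nothing about what the evaluator knows.

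**The concern.** Separate rooms keep the evaluator from watching the procedure. They do not keep the evaluator from seeing what the procedure leaves behind. The evaluator places or works from the skin mark, presses the point before treatment, and looks at and presses it again shortly afterwards. In one arm that skin has been wiped, punctured and given hemostasis in the interval; in the other, the described handling was elsewhere on the leg. A puncture mark, redness or a smeared skin mark could give the arm away.

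Algometry is performed by the evaluator, so knowing the arm could influence the reading. If it does, the shift differs by group and appears only after the intervention. The SAP's repeated-measures ANCOVA compares groups over the four times, and a differential observer shift would enter it in the same form as a treatment effect. Age, sex, body mass index and physical activity, the covariates the protocol names, cannot remove it. At stake is the specific objective on whether needling is effective for the trigger point, which algometry appears to serve.

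**Working it through.** **Step 1. What happens at the measured point, by arm**

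| Step | G1 | G2 |
|---|---|---|
| Palpation, skin mark, three baseline readings | yes | yes |
| Alcohol during intervention | at the marked point | at the sham area |
| Needle | into the marked point | none described; guide tube at the sham area |
| Hemostasis | at the needled area | simulated, at the sham area |
| Return to the evaluator | immediately | immediately |

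The arms match until the intervention step and differ at the measured point after it.

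**Step 2. What would stop the evaluator inferring the arm?** I looked in the protocol and SAP for five safeguards: a statement that the evaluator is unaware of allocation, a cover over the site, matched handling of the marked point in G2, an instruction to subjects not to say what was done, and a record of the evaluator's guess. None is there.

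**Step 3. Which outcomes are exposed?** Algometry is exposed, since the evaluator applies it at the treated site. The goniometric measurements listed for 24 h and 72 h would also be exposed if the same evaluator takes them. Baropodometry is recorded by a platform while the subject walks for one minute, which leaves the evaluator much less room to influence it.

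**Step 4. Size, as an illustration.** The plan gives no sample size, SD, effect or power, so there is no figure to reproduce. Assume a two-sample t-test, two-sided at 5%, no true effect, n subjects per group, and an evaluator shift of b SD between arms, where SD is that of the compared measure.

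- Noncentrality: δ = b × √(n/2), with 2n − 2 degrees of freedom.
- Rejection rate: P(|T| > t₀.₉₇₅), with T noncentral t.

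| n per group | b | δ | df | critical t | rejection rate |
|---|---|---|---|---|---|
| 20 | 0 | 0 | 38 | 2.024 | 5% |
| 20 | 0.2 | 0.632 | 38 | 2.024 | about 9.5% |
| 20 | 0.4 | 1.265 | 38 | 2.024 | about 23% |
| 40 | 0 | 0 | 78 | 1.991 | 5% |
| 40 | 0.2 | 0.894 | 78 | 1.991 | about 14% |
| 40 | 0.4 | 1.789 | 78 | 1.991 | about 42% |

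Both n and b are assumed. With no shift the rate stays at 5%. For a fixed shift, a larger trial makes the false finding more likely.

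**The case against.** The strongest reply is that the protocol never claims the evaluator is blinded. The setting text describes rooms, distance and temperature and does not present them as a masking device, so no stated claim is contradicted. That stands: the finding is an absent safeguard, not a false statement.

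A reader might go further than the text allows in three other ways.

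- *That the point is untouched in G2.* It is not. The evaluator palpates, marks and presses it at baseline in both arms, so signs of pressing alone would not separate the groups. The contrast lies in the alcohol, the needle and the hemostasis.
- *That the evaluator will know the arm.* No passage describes a visible trace, and that hemostasis means pressure is an inference. Repeat algometry at the same point is implied but not spelled out. Traces are plausible, most of all at the immediate reading; at 24 h and 72 h the skin may have recovered, and the issue is then mainly what the evaluator remembers.
- *That the whole trial is compromised.* The general objective is plantar pressure, recorded by a platform.

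It can also be said that the algometer and its stopping rule are not described, so how far an evaluator could shift a reading is unknown, and that the illustration uses a simpler test than the planned ANCOVA. Both are fair. They limit the size that can be claimed. They do not remove the asymmetry at the measured site, which follows from carrying out the procedures as written.

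**Conclusion.** The point holds for algometry. Evaluator blinding is neither stated nor secured, and the two-room arrangement cannot be relied on to provide it, because the measured site is treated in G1 only and the same evaluator returns to it immediately. The arm may be revealed at the first post-intervention reading and the knowledge carried forward.

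The conclusion rests on two inferences: that needling can leave a recognisable trace, and that an evaluator who suspects the arm can influence an algometer reading. The size is unknown. About 10% to 42% false positives, against a nominal 5%, describes the assumed shifts and group sizes and is not an estimate for this trial. Baropodometry, and so the general objective, is largely unaffected. This is a change the sponsor should make because it is cheap and protects a stated specific objective; it is not a fatal flaw.

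**What to change.** Amend the intervention and setting text as follows.

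1. In both arms, the person delivering the intervention places an identical thin opaque adhesive cover, centred on the skin mark, before the subject returns to the evaluator. The same kind of cover is applied before the 24 h and 72 h readings. All post-intervention algometry is taken through it.
2. State that the evaluator is not told the allocation.
3. Instruct subjects not to discuss the procedure with the evaluator.
4. Record the evaluator's guess of the arm and report it by group.

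This fix should not add compression at the marked point in G2, since that would alter the comparator at the site of the outcome. Separately, the sponsor should reconcile or justify the different sites used in the two arms; the G1 text works at the tibialis posterior, whereas the G2 text "simulates the technique of puncture in the right twin of the subject".

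**Cost.** Three adhesive covers per subject (one for each of the three post-intervention readings), a little time, and a few sentences of protocol. The downside is that readings are taken through a thin layer, equally in both arms, and that the cover must be centred on the mark because it then guides where the evaluator presses. The mark must also still be findable at 24 h and 72 h, which the protocol does not address.

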### **Statistical Analysis Plan (SAP)**

For the qualitative variables we will make some frequency tables. On the other hand, for the quantitative variables, maximums, minimums, mean values and the standard deviation will be calculated.

To check the homogeneity of the intervention and control groups, the association with the explanatory variables sex, age, body mass index and sport hours will be measured using the Chi-square test or the T-student test as appropriate.

The equality of mean values of each dependent variable will be tested, both in the intervention group and in the control group, as in the four measurement times by means of an ANCOVA procedure (analysis of the covariance with repeated measures).

The confidence interval will be 95%

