#### General:

- Evidence changes in pressure in the plantar support in dynamics after treatment with deep dry needling in the tibialis posterior myofascial trigger point.

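### The SAP's only outcome test counts the pre-intervention value among its four times and names neither a between-group post-intervention contrast nor adjustment for that value

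*Combined protocol and SAP*

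**What the plan says.** The Statistical Analysis Plan has one sentence on outcome inference. For each dependent variable it tests equality of means "both in the intervention group and in the control group, as in the four measurement times by means of an ANCOVA procedure", which it labels a repeated-measures analysis of covariance. It does not list the four times, and it names no covariate in that sentence.

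The times come from the procedures that follow the Specific objectives. Algometry and baropodometry are done before treatment ("Once the pre-intervention measurements have been made", the subject moves to the treatment room). Next comes "the evaluation immediately after the intervention (POSTINT), both algometric and baropodometric measurements", and then visits at 24 h and 72 h.

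The rest of the SAP does not fill the gap. For the check of group homogeneity, "the association with the explanatory variables sex, age, body mass index and sport hours will be measured" with chi-square or t tests. The sentence "The confidence interval will be 95" (per cent) is attached to no quantity.

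Three objectives bear on the point:
- General: "Evidence changes in pressure in the plantar support in dynamics after treatment with deep dry needling", with no mention of the control group.
- Specific: "Analyze the variation of the plantar dynamics in the subjects without intervention to avoid learning bias of the methodology of the baropodometric registry".
- Specific: look for "differences in the treatment taking into account the covariates measured such as age, sex, and physical activity practice and body mass index".

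**The concern.** A repeated-measures model with two groups and four times yields a group effect, a time effect and a group-by-time interaction. They answer different questions, and the plan does not say which one decides whether needling works.

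- **Group-by-time.** This compares change between arms and is valid. With four occasions it is a 3-df test and gives no single effect estimate. It does not adjust for PRE, so it usually gives up some precision.
- **Group main effect over all times.** PRE cannot carry a treatment effect, so averaging it in dilutes the estimate. A chance difference between arms at baseline also enters the estimate.
- **Time effect or within-arm tests.** These do not compare the arms. The second objective itself anticipates learning on the baropodometer. Both arms would share such a shift, and only a between-group contrast removes it.

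The PRE value is already collected. Using it as a covariate would give an undiluted estimate to which the 95% interval can be attached, and would leave less room to choose a result after the data are seen.

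**Working it through.** **Counting the times.** PRE, POSTINT, POST24h and POST72h make four. Without PRE there are three. So PRE is an outcome level, by count; the SAP does not say so directly.

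**Occasions per variable.** Algometry is listed at all four times. Baropodometry is listed at PRE and POSTINT. For 24 h and 72 h the procedures list algometric and goniometric measurements. As written, plantar pressure therefore has two occasions, while the SAP speaks of four times for each dependent variable. Both cases are worked below.

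**Inputs.** The documents give no sample size, SD, correlation, effect size or power, so there is no figure to reproduce. Assumed: unit variance, a common correlation r between occasions, equal PRE means in expectation, an effect d at every post time, normal approximation, two-sided 5% (inferred from the 95% interval). The scale is set so that a PRE-adjusted comparison at one post time has 80% power, that is, noncentrality L = 7.849. Its variance factor is 1 − r².

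**Noncentrality on that scale.**
- Group-by-time, four occasions (3 df): 0.75d²/(1 − r) per unit of information, so 0.75·L·(1 + r). At r = 0.5: 0.75 × 7.849 × 1.5 = 8.83, power 70%.
- Group-by-time, two occasions (1 df, the difference in change): variance 2(1 − r), so L(1 + r)/2. At r = 0.5: 5.89, power 68%.
- Group main effect, four occasions: estimate (0 + d + d + d)/4 = 0.75d, variance (1 + 3r)/4, so 2.25·L·(1 − r²)/(1 + 3r). At r = 0.5: 5.30, power 63%.
- Group main effect, two occasions: estimate 0.5d, variance (1 + r)/2, so 0.5·L·(1 − r). At r = 0.5: 1.96, power 29%.
- Mean of three post values minus PRE, unadjusted (1 df): variance 4(1 − r)/3, so 0.75·L·(1 + r), the same noncentrality as the 3-df test.
- Mean of three post values adjusted for PRE (1 df): variance (1 − r)(1 + 3r)/3, so 3·L·(1 + r)/(1 + 3r).

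| Power (%) | r = 0.3 | 0.5 | 0.7 | 0.8 |
|---|---|---|---|---|
| PRE-adjusted, one post time (reference) | 80 | 80 | 80 | 80 |
| Group-by-time, four occasions, 3 df | 63 | 70 | 76 | 79 |
| Group-by-time, two occasions, 1 df | 62 | 68 | 73 | 76 |
| Group main effect, four occasions | 83 | 63 | 40 | 28 |
| Group main effect, two occasions | 38 | 29 | 19 | 14 |
| Mean post minus PRE, unadjusted, 1 df | 79 | 84 | 89 | 90 |
| Mean post adjusted for PRE, 1 df | 98 | 96 | 95 | 94 |

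At r = 0.9, group-by-time has 81% with four occasions and 78% with two.

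**Baseline imbalance.** A chance baseline difference b shifts the main-effect estimate by (1 + 3r)/4 × b with four occasions, which is 0.48b/0.63b/0.78b/0.85b. With two occasions the shift is (1 + r)/2 × b, which is 0.65b/0.75b/0.85b/0.90b. The PRE-adjusted estimate shifts by about 0.

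**Within-arm reading.** In a simulation with an assumed 20 per arm, no treatment effect and an assumed shift of 0.4 SD shared by both arms, only G1 showed a significant PRE-to-POSTINT change in 21/24/24/18% of trials. The between-group tests stayed at 4.8–5.2%.

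**The case against.** The strongest reply is that a statistician would read the sentence as a group-by-time analysis, which is valid. The loss is then modest: 1 to 4 points at r = 0.7–0.8 with four occasions, and none at r = 0.9. This stands.

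A second reply is that the four-occasion comparison sets a 3-df omnibus test against a focused 1-df test. This also stands. The unadjusted 1-df contrast of mean post minus PRE has the same noncentrality as the 3-df test, yet reaches 79–90%. That step owes nothing to baseline adjustment. Adjustment accounts for the further step to 94–98%. With two occasions both tests have 1 df, so the shortfall there (80% against 62–76%) is due to the missing adjustment alone.

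Third, a single-time contrast is not always the best choice. For a constant effect the adjusted average of the post times is clearly stronger. If the effect occurs only at a post time other than the one named, a single-time test has about 5% power, while group-by-time keeps its power. The contrast should therefore be the sponsor's choice.

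Fourth, the four-occasion figures do not describe plantar pressure as the procedures now read. This stands, and it is why both cases are shown.

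A reader might go further and infer that the plan intends to judge needling by change within G1, because the general objective mentions no control. The documents do not support that: the SAP sentence covers both groups, and the learning objective shows that the authors had shared change in mind. The wording leaves the within-arm reading open; it does not adopt it.

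**Conclusion.** The point holds as under-specification with a better method at hand. The only outcome-inference sentence makes PRE an outcome level, names no between-group post-intervention contrast as the treatment test, and does not name PRE as a covariate. The baseline chi-square and t tests supply neither.

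On the natural group-by-time reading, power is 63/70/76/79% with four occasions and 62/68/73/76% with two, against 80% for a PRE-adjusted single-time comparison at r = 0.3/0.5/0.7/0.8. All of this rests on assumed correlations, equal variances and a constant effect. The efficiency loss is usual, not universal.

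A reader might take the lowest main-effect figures, or the 18–24% rate of change in G1 only, as the expected performance of this plan. They are not. They belong to readings that the text leaves open but does not state, and the within-arm rates also need an assumed sample size and shift. Nor is 0.75d a fixed dilution: it is 0.5d for a variable measured only at PRE and POSTINT, and it arises only if the group main effect is taken as the treatment test. This should be fixed before analysis; it is not evidence that an invalid test was planned.

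**What to change.** Replace the ANCOVA sentence with wording to this effect:

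> For each dependent variable, the post-intervention values at the times at which it is measured will be analysed in a repeated-measures model with group, time, group-by-time, the PRE value and PRE-by-time. The treatment test is the PRE-adjusted G1 minus G2 difference with its 95% confidence interval. Within-group changes are descriptive.

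A model that keeps PRE as an outcome but constrains its mean to be equal in both groups is an acceptable equivalent. Before analysis the sponsor should state whether the contrast is at one post time or averaged over the post times, and for which dependent variable it decides. The remaining times and variables are secondary. For a variable measured only at PRE and POSTINT, the model reduces to one PRE-adjusted comparison at POSTINT.

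The SAP should also say whether age, sex, physical activity and body mass index enter as adjustment covariates. If the covariate objective means effect modification, it belongs in a separate secondary analysis.

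Reconcile the procedures (algometric and goniometric measurements at 24 h and 72 h) with the SAP (four times for each dependent variable), because the number of occasions for plantar pressure depends on it.

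Cost: text only. PRE is already measured, so no new data are needed. The model spends one degree of freedom on PRE, and up to three with PRE-by-time over three post times. No sample size is stated, so that cost cannot be called nil, but it would matter only in a very small trial.

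### The repeated-measures ANCOVA has no estimation method, analysis population or missing-data rule; its classical form would discard every subject who misses one return visit

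*Combined protocol and SAP*

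**What the plan says.** The *Statistical Analysis Plan (SAP)* section gives one inferential procedure. Mean values of every dependent variable are compared between intervention and control, "as in the four measurement times by means of an ANCOVA procedure (analysis of the covariance with repeated measures". The only other specification for this analysis is the 95% confidence level. The section names no estimation method, analysis population or rule for missing values.

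The measurement times are set out in the procedure text of the protocol, which follows the heading *Specific*. Pre-intervention values (PRE below) and the values from "the evaluation immediately after the intervention (POSTINT), both algometric and baropodometric measurements" are taken on the day of the intervention. Afterwards "the subject will be summoned at the same time to return at 24 hours (POST24h) and at 72 hours (POST72h", in each case "to perform the corresponding algometric and goniometric measurements". Baropodometry is named before and immediately after the intervention, but not at 24 h or 72 h.

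Allocation is random: "a randomization (Epidat V4.0) of the selected subjects will be carried out to assign them to one of the intervention groups". The specific objectives also ask for treatment differences to be examined with age, sex, physical activity and body mass index taken into account.

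**The concern.** PRE and POSTINT are collected in one session, so nearly every randomised subject should have both. POST24h and POST72h each depend on the subject coming back. Classical repeated-measures ANCOVA holds one row per subject with four outcome columns and, by default, deletes a row with any gap. A single missed visit then removes three values that were observed: PRE, POSTINT and the other follow-up. The immediate comparison would lose subjects for whom it is fully observed.

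Two things are at stake. The first is precision, which is lost even when missingness is purely random. The second is the randomised comparison itself. Group 1 receives a needle moved repeatedly in and out of the trigger point, while the control group receives a simulation with a guide tube over a different muscle. Reasons for not returning could therefore differ between arms. If they also relate to outcome, a completers-only comparison no longer compares the groups as randomised.

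**Working it through.** The plan states no sample size, dropout rate or variance, so there is no figure of its own to reproduce. All rates below are assumptions.

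**1. Subjects lost by deletion of incomplete rows.** Let m be the share of subjects missing each return visit. If the same subjects miss both visits, the loss is m. If misses are independent, it is 1 − (1 − m)². The standard error of the POSTINT contrast, for which complete data would exist, grows by the factor 1/√(1 − loss).

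| m | Loss, same subjects | SE factor | Loss, independent misses | SE factor |
|---|---|---|---|---|
| 5% | 5% | 1/√0.95 = 1.03 | 1 − 0.95² = 9.75% | 1/√0.9025 = 1.05 |
| 10% | 10% | 1/√0.90 = 1.05 | 1 − 0.90² = 19% | 1/√0.81 = 1.11 |
| 15% | 15% | 1/√0.85 = 1.08 | 1 − 0.85² = 27.75% | 1/√0.7225 = 1.18 |

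**2. Bias when missingness depends on observed values.** Large-sample simulation with 200,000 subjects per arm, SD 1, equal correlation of 0.5 or 0.7 between times, no true arm difference, and 9–10% missing at each return visit. Where missingness depended on outcome, its probability was 1/(1 + exp(2.8 + 1.2 × POSTINT)); otherwise it was 10% at random.

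| Missingness | Completers, unadjusted | Completers, adjusted for PRE | Likelihood, all available data |
|---|---|---|---|
| Completely at random | about 0 | about 0 | about 0 |
| Depends on POSTINT, same way in both arms | about 0 | about 0 | about 0 |
| Depends on POSTINT, needling arm only | 0.09 to 0.18 SD | 0.10 to 0.14 SD at POSTINT; 0.04 to 0.05 SD at 24 h and 72 h | within 0.006 SD of 0 |

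The sign follows the assumed dependence. In a separate run (correlation 0.6, 10% loss in the needling arm, 5% random loss in control, logistic slope 1 per SD of POSTINT-minus-PRE change), the completers' difference in change from PRE was wrong by about 0.07 SD. Making improved subjects the ones who stay away reversed its direction.

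**3. Bias when missingness depends on a value never observed.** Same set-up, but loss in the needling arm depends on the 72 h change from PRE, and the true 72 h difference is 0.50 SD.

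| Needling-arm loss (slope) | Completers | Likelihood | Share of bias remaining |
|---|---|---|---|
| 10% (1.0) | 0.57 | 0.55 | 0.05/0.07, about 70% |
| 20% (1.5) | 0.69 | 0.63 to 0.64 | 0.13/0.19 to 0.14/0.19, about 70% |

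In this case the mixed model removes only part of the bias.

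**4. Which outcomes have four values.** Algometry is named before the intervention, at POSTINT, at 24 h and at 72 h, which makes four. Baropodometry is named only before the intervention and at POSTINT, which makes two. Goniometry is named only at 24 h and 72 h. The SAP nevertheless applies four times to every dependent variable.

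**The case against.** The strongest reply is that the SAP never says only complete cases are used. That is correct. A reader might infer that the plan commits to a completers-only analysis, but the text gives no estimation method, and a mixed model on one-record-per-visit data would also fit its wording and would keep partial records. The defect is that the choice is open, and that the default of the named procedure in its classical form is deletion.

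A reader might also infer that the result would be tilted towards needling. The documents do not support a direction. They report no attrition and no sign of differential loss, and bias arises only if missingness is related to outcome and differs by arm. Over 72 hours the loss may be small.

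Nor do the documents suggest that a subject who misses 24 h is left out at 72 h: every subject is called for both visits, with no condition attached.

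Finally, plantar pressure, the subject of the general objective, has no named 24 h or 72 h measurement. Read literally, a missed return visit removes nothing from it. This limits the point to outcomes measured at all four times. For algometry the point stands.

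**Conclusion.** The point holds as a gap in specification with a foreseeable consequence. If the ANCOVA is run in its classical form, subjects with one missed visit are lost from every contrast, including the immediate one. The loss is 5% to 28% of subjects across assumed per-visit miss rates of 5% to 15%, depending on whether misses coincide. Bias is possible but not shown. In the scenarios where missingness depended on POSTINT in one arm only, with no true effect, it was 0.04 to 0.18 SD. It was about zero under random missingness or the same mechanism in both arms. These sizes rest on assumed rates, correlations and missingness models, none of which comes from the documents. A likelihood analysis is the better choice because it needs only missing-at-random, a weaker condition than the completers analysis requires. It does not protect fully against loss driven by unobserved later values.

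**What to change.** In the SAP, replace the unspecified repeated-measures ANCOVA with a linear mixed model for repeated measures. It should contain group, time, group-by-time, an unstructured within-subject covariance, and the covariates from the specific objectives (age, sex, physical activity and body mass index). Fit it by restricted maximum likelihood to every available measurement of every randomised subject, in the assigned group. State that the analysis assumes data are missing at random.

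Reconcile the procedure text with the SAP on which outcomes are measured at 24 h and 72 h, so that the number of times in each outcome's model is clear.

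The cost is wording only: no extra subjects, visits or staff. With complete data the two analyses give nearly the same answer. The small downside is the reliance on missing-at-random described above.
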